# Time-Varying Cox Regression Models (Secondary Clinical Objectives)

Time-varying Cox models will be used to compare the time to stroke/SE, major bleeding, and death between: 1) treated vs untreated; 2) each OAC vs untreated after inverse probability treatment weighting. Treatment will be used as a time varying covariate, in order to account for the untreated period of an ever-treated patient. Weights generated using IPW will be incorporated.

# Marginal Structural Models (MSMs; Secondary Cost Objective)

A weighted generalized estimating equation (GEE) models will be applied for the multivariate analysis of health care costs among: treated vs untreated; 2) each OAC vs untreated. For cost outcomes, gamma distribution and a log link will be used. IPW weights will be incorporated to adjust for baseline covariates and any time dependent confounders. Time-dependent confounders will not be included in the repeated measures model – as their effects have been incorporated into the weights. Treatment will be included as a time-dependent variable, and time-invariant covariates may be included based on results of IPW and clinical rationale.

All data analysis will be executed using the statistical software SAS version 9.4.

Do not distribute for purposes outside of specific activities related to development of FDAMAs114 compliant pieces. Content within this protocol is subject to change based on communication planning and input by external review committees.

Apixaban NON-INTERVENTIONAL STUDY PROTOCOL

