#### Apixaban NON-INTERVENTIONAL STUDY PROTOCOL

- 4. Compare the risk of death among elderly patients treated versus untreated with OACs in the Medicare NVAF population.
- 5. Compare the all-cause health care costs among elderly patients treated versus untreated with OACs in the Medicare NVAF population.

**Study Design:** The study will be a longitudinal retrospective cohort analysis using the US Centers for Medicare & Medicaid Services (CMS) Medicare dataset from 01JAN2012-31DEC2016. The study will designate a 12-month baseline period prior to the identification period (01JAN2013-31DEC2016). This database only includes patients enrolled in fee-for-service (FFS) Medicare; those enrolled in managed-care plans will be excluded. Further, patient eligibility will be based on selection from the database according to the following inclusion and exclusion criteria (sections 2).

**Population:** Elderly patients (aged  $\geq 65$  years) will be required to have  $\geq 1$  inpatient or  $\geq 2$  outpatient medical claims (the 2 outpatient claims are  $\geq 7$  days apart) for AF during the identification period for the primary and secondary objectives. For the primary objective, two mutually-exclusive NVAF patient cohorts will be created: ever-treated with OAC and never-treated with OAC. For the secondary objective assessing clinical and healthcare utilization and costs, treatment status will be a time-varying covariate and ever-treated patients will contribute time-not-on-treatment to untreated effect.

For the primary and secondary objectives, the ever-treated with OAC population cohort will include newly diagnosed NVAF patients who ever initiated oral anticoagulant (OAC) treatment (apixaban, dabigatran, edoxaban, rivaroxaban, and warfarin) during the study period identified from 01JAN2013-31DEC2016. The never-treated with OAC population cohort will include newly diagnosed NVAF patients without any OAC claim from 01JAN2013-31DEC2016.

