# 8.2. Setting

Ever treated with OAC and never treated with OAC patients will be selected from 01JAN2013-31DEC2016. To ensure access to the patients' complete medical history, they will be required to have continuous health plan enrollment for the 12 months before the first AF diagnosis date/index date (baseline period). Patient data will be assessed from index date until the earliest of death, health plan disenrollment, treatment switch (treated patients), discontinuation (treated patients), or 31DEC2016 (end of study).

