# Inverse Probability Weighting (IPW; Secondary Objectives)

Do not distribute for purposes outside of specific activities related to development of FDAMAs114 compliant pieces. Content within this protocol is subject to change based on communication planning and input by external review committees.

Pfizer Confidential

Page 28 of 37

Apixaban NON-INTERVENTIONAL STUDY PROTOCOL

IPW uses propensity scores to obtain estimates of the average treatment and censoring effect. Propensity scores will be calculated using repeated measures logistic models with: 1) ever-treated with OAC and never-treated with OAC cohorts; 2) each DOAC treated and never-treated with OAC cohorts included in the model, using never-treated patients as the reference (i.e. control cohort). Appropriate correlation structure will be chosen based on the data and clinical rationale.

The propensity score is defined as the probability of a patient receiving OAC/DOAC treatment or being censored conditional on both time-dependent covariates (e.g., comorbidities) and time-independent baseline covariates (age, gender, race, and baseline value for each of the time-dependent variables). The list of variables included in the logistic model will be based on clinical rationale. The propensity score acts as a balancing score among the cohorts.

After calculating the propensity score, the distribution of the propensity scores will be reviewed.

Each patient's weight is equal to the inverse of the probability of their treatment option and censoring (weight=1/propensity score). The numerator of the weight is the propensity score that a patient is on observed treatment/censored in a time period conditional on the baseline covariates. Denominator of the weight is the same propensity score conditional on time-dependent (factors such as CHA2DS2-VASc score, history of bleeding, etc.) and time-independent confounders. If an ever-treated patient has a very low propensity score, a very large weight can be created. Large weights can increase the variability of estimated treatment effect. In order to address this, the weights will be stabilized. Stabilized weights for treatment and censoring will be calculated for each time period of a patient. This reduces the variability of the weights.

$$SW = \prod_{k=0}^{t} \frac{f[A(k) | \overline{A}(k-1), V]}{f[A(k) | \overline{A}(k-1), \overline{L}(k)]}$$

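### The cost GEE lists no term for time since AF diagnosis, so the part of a shared cost trend that tracks the changing treated share enters the all-cause OAC cost ratio

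*Protocol*

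**What the plan says.** Protocol Section 8.7, under Marginal Structural Models, sets out the cost analysis as a weighted GEE.

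- **Family and link:** "For cost outcomes, gamma distribution and a log link will be used".
- **Terms in the model:** "Treatment will be included as a time-dependent variable, and time-invariant covariates may be included based on results of IPW and clinical rationale".
- **Left to the weights:** "Time-dependent confounders will not be included in the repeated measures model".

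The weights come from the Inverse Probability Weighting part of the same section: "Stabilized weights for treatment and censoring will be calculated for each time period of a patient". The numerator is described as the probability that "a patient is on observed treatment/censored in a time period conditional on the baseline covariates". The printed formula also conditions it on treatment history.

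Three other places fix how patient time is divided:

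- The Abstract makes the first AF diagnosis the index date for both cohorts.
- The Abstract (Population) says that "ever-treated patients will contribute time-not-on-treatment to untreated effect".
- Section 8.2 sets the end of follow-up: "Patient data will be assessed from index date until the earliest of death, health plan disenrollment, treatment switch (treated patients), discontinuation (treated patients"), or the end of the study on 31 December 2016.

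Table 3 defines all-cause costs per person per month. The stroke/SE- and bleeding-related costs are defined as the cost of the first such hospitalization.

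**The concern.** The terms listed for the cost model are treatment and, optionally, covariates that do not change over time. None of them can carry a cost curve that rises or falls with time since diagnosis. If treated and untreated months lie at different distances from diagnosis, the treatment coefficient has to absorb part of that curve.

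The rules on patient time make such a difference likely. Early months before the first fill go to the untreated side. Treated patients leave at switch or discontinuation, whereas never-treated patients can stay to the end of the study.

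A cost peak near time zero is also plausible from the protocol itself. One inpatient AF claim is enough to qualify, and the first AF claim sets the index date (Section 8.2.1.1). Baseline excludes the index date (Section 8.3), and data are assessed from it (Section 8.2), so the qualifying admission may fall into follow-up. Section 6 puts hospitalizations at 52% of AF costs.

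At stake is the all-cause cost ratio of secondary objective 5, which could show a saving or an excess when OAC has no effect on cost. No planned check would reveal this. The balance diagnostics look at covariates, and the 6-month censoring analysis in Section 8.8 is limited to the clinical outcomes. The Cox models measure time from index and do not share the problem.

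**Working it through.** The protocol states no cost effect, cost variance or cost trend, so there is no figure of its own to reproduce. The check sets the true OAC cost ratio to 1.00 and asks what the listed model returns.

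**Step 1: what the listed model estimates.** Let c(k) be the mean cost in month k after diagnosis, the same for everyone, and let T(k) and U(k) be the numbers of treated and untreated patients in that month. A log-link gamma model with treatment as its only term, and independence working correlation (assumed, as none is stated for this GEE), gives

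estimated ratio = [Σ T(k)c(k) / Σ T(k)] ÷ [Σ U(k)c(k) / Σ U(k)].

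This equals 1 for any start and stop pattern if c(k) is flat, and for any cost curve if T(k)/U(k) is constant. Otherwise it generally differs from 1. With a term for each month, the contrast is within month: c(k)/c(k) = 1.

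**Step 2: why the weights do not remove it.** Suppose there is no confounding. The numerator and denominator of the stabilized weight are then equal, every weight is 1, and Step 1 applies unchanged. Leaving time out of the numerator does not help either. A constant monthly start probability still makes the treated share grow with time.

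**Step 3: numbers (all assumed).** Cost curve c(k) = 1 + (R − 1)·exp(−k/2), with k = 0 in the first month and R the ratio of first-month to later cost. Each month 1% of patients leave, a fraction h(k) of untreated patients start, and a fraction d of treated patients discontinue and are censored:

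U(k) = 0.99·U(k−1)·[1 − h(k)]; T(k) = 0.99·(1 − d)·T(k−1) + 0.99·U(k−1)·h(k).

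At k = 0, U = 1 − h(0) and T = h(0). Results for R = 2:

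| Start pattern | d | Months | Mean untreated cost | Mean treated cost | Ratio |
|---|---|---|---|---|---|
| 3% every month | 0 | 24 | 1.153 | 1.029 | 0.892 |
| 20% in first month, 5% in next five, then 1% | 5% | 48 | 1.090 | 1.074 | 0.985 |
| 40% in first month, 2% in next five, then 0.5% | 5% | 48 | 1.076 | 1.119 | 1.040 |

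In the first row with d = 0, the treated share is 1 − 0.97 = 3% in the first month and 1 − 0.97^24 = 52% in the last. Treated months therefore lie late, where cost is low. In the third row the share starts at 40% and falls through discontinuation, so the sign reverses.

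A fourth pattern had no starts in the first month, 5% in the next five and then 1%. Over all four patterns, d of 0 or 5%, and 12, 24 or 48 months:

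| R | Range of estimated ratio |
|---|---|
| 1 | 1.00 throughout |
| 1.5 | 0.92 to 1.02 |
| 2 | 0.86 to 1.04 |
| 4 | 0.71 to 1.10 |

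**Step 4: a second set of assumptions.** This used simulated gamma costs with first-month cost twice the later level, a 3-month half-life, and no confounding.

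- Constant 4% monthly starts, mean 12 months to discontinuation: 0.88.
- 40% starting in the first month, mean persistence 6 months: 1.19.
- Declining start rate, mean 12 months: the opposing effects nearly cancel, at 0.98 to 1.00 across first-month cost ratios of 1.5, 2 and 3.
- Period indicators added: 0.99 to 1.00 in every scenario at 2,000 patients.

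Together with Step 3, a doubled first-month cost gives roughly 0.86 to 1.19.

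**Step 5: with confounding and weights.** This used 60,000 simulated patients, 24 months, one time-varying confounder, stabilized weights of the protocol's form, and R = 2.

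| Weight numerator | No month terms | Month terms in cost model |
|---|---|---|
| Includes time | 0.936 | 0.998 |
| Omits time | 0.896 | 0.997 |

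**The case against.** The strongest reply is that Section 8.7 prints no regression equation. It keeps out time-dependent confounders, such as comorbidities, and says nothing either way about a period index. A statistical analysis plan that is not shown could add one. This stands as a limit: the protocol omits the term and does not forbid it. But the section does more than outline. It names estimator, distribution, link and regressors, and it explains why time-varying factors are left to the weights. Someone following it would fit treatment and baseline covariates only.

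The sizes rest wholly on assumed cost curves and start and stop rates. That stands too. The cost analyses are also secondary, Section 8.7 makes objectives 2 to 5 optional, and the limitations section claims associations only. This lowers the stakes, but an association distorted by follow-up time is still not the one intended.

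A reader might infer more than the documents support:

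- **That every shared change in cost is counted as an OAC effect.** Only the part aligned with the changing treated share is. The near-cancelling scenarios show this.
- **That stroke/SE- and bleeding-related costs are biased in the same way.** The Abstract does apply these models to them, but Table 3 defines them as first-hospitalization costs, and the calculations above use costs in every month. They do not represent that outcome.
- **That the drug-specific ratios will differ spuriously.** This could happen if start and persistence patterns differ by drug, but no such rates are given.
- **That false-positive rates can be read off at the sample sizes of Section 8.5.** Those totals were computed for stroke/SE and bleeding. In a large enough sample any non-zero bias becomes significant.

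**Conclusion.** The point holds for all-cause per-month costs. As listed, the cost GEE has no term for time since index, the stabilized weights do not make treatment independent of that time, and the follow-up rules make the treated share change with it. Fitting the model as listed can therefore give a biased OAC cost ratio.

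The bias is zero with flat costs and can be close to zero when early starts and discontinuation offset each other. Its sign depends on how soon patients start and how long they persist. The range of roughly 0.86 to 1.19 for a true ratio of 1.00 is conditional on a first-month cost twice the later level and on the start and stop patterns given. It shows that the error can matter; it does not predict its size in this study.

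**What to change.** In Section 8.7, Marginal Structural Models, add time since index date as a main effect in the weighted GEE, either as period indicators or as a spline of months:

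log E[cost in period k] = b0 + f(k) + b1·A(k) + baseline covariates.

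Here A(k) is treatment in period k, and b1 then compares treated with untreated patients at the same time after diagnosis. In the Inverse Probability Weighting part, put the same time term in both the numerator and the denominator models. Apply the change to all-cause costs, and to stroke/SE- and bleeding-related costs only where these are analysed as repeated per-period costs.

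This takes a sentence or two of text and no new data. The price is a few more parameters and a slightly wider interval for b1, which should be small in the 100% Medicare file.

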# 8.8. Subgroup and Sensitivity Analysis

Additional subgroup and sensitivity analyses will be conducted, including:

- high-risk CHA2DS2-VASc score subgroups, specifically, 2-3, 4-5, and ≥6 (primary objective): assess whether the predictors of treatment would be impacted by baseline CHA2DS2-VASc score.
- high-risk age subgroups, specifically, 65-74, 75-79, and  $\geq$ 80 years (primary objective): assess whether the predictors of treatment would be impacted by age.
- censor patients at 6 months (secondary clinical objectives): assess whether the differential follow-up time in each cohort would affect the clinical outcomes.
- use a certain allowable gap for drug exposure, such as 14 days (secondary clinical objectives): assess whether the allowable gap in OAC days of supply for treated patients would have an impact on the clinical outcomes, since a shorter allowable gap will increase the likelihood of having the patients truly on treatment.
- multivariable Cox regression (secondary clinical objectives): assess whether statistical methods on the multivariable analysis would affect the clinical outcomes.
- adjusting for the competing risks of death (secondary clinical objectives): assess whether death is a competing risk in the clinical outcome analyses.

# 8.9. Quality Control

# 8.10. Standard STATinMED quality control procedures will be used. Research Methods Strengths and Limitations

This study will use the 100% Medicare Database, a large national database representative of the US population. The sample size will be large enough to analyze detailed demographic and clinical characteristics of patients, health outcomes, treatment patterns, and health care utilization and costs.

The study is limited by the nature of claims data, which may be constrained by issues such as over-the-counter use of aspirin, incorrect coding, claims without actual medicinal treatment, and other incomplete claims information. Moreover, although patients will be matched on baseline demographic and clinical characteristics, given the nature of retrospective observational studies, residual confounders may still exist, especially between the ever treated versus never treated NVAF patients. As a result, only associations between variables can be studied, without assessment of causal relationships. In addition, given the differences between the ever treated and never treated populations and the results from the primary objective for

Pfizer Confidential

Page 31 of 37

Do not distribute for purposes outside of specific activities related to development of FDAMAs114 compliant pieces. Content within this protocol is subject to change based on communication planning and input by external review committees.

Apixaban NON-INTERVENTIONAL STUDY PROTOCOL

the predictors of treatment, the comparative analyses for stroke/SE, major bleeding, and health care costs in the secondary objectives may not be feasible. Comorbidities at baseline (eg, presence of renal impairment) will be determined only by the presence of ICD-9-CM and ICD-10-CM diagnosis codes in the baseline period, not based on actual lab values or clinical assessment. Finally, warfarin treatment is continuously dose-adjusted so there is no low or high-dose strategy that can be defined.

# 8.11. Other Aspects

Not applicable.

# 9. **Protection of Human Subjects**

# 9.1. Patient Information and Consent

As a secondary data collection study using fully anonymized data, informed consent is not required.

# 9.2. Patient Withdrawal

Not applicable.

# 9.3. Institutional Review Board/Independent Ethics Committee

Institutional Review Board/Independent Ethics Committee review is not required.

# 9.4. Ethical Conduct of the Study

The study will be conducted in accordance with legal and regulatory requirements, as well as with scientific purpose, value and rigor and follow generally accepted research practices described in Guidelines for Good Pharmacoepidemiology Practices (GPP) issued by the International Society for Pharmacoepidemiology (ISPE).

# **10.** Management and Reporting of Adverse Events/Adverse Reactions

This study involves unstructured data that exist as structured data by the time of study start or a combination of existing structured data and unstructured data, which will be converted to structured form during the implementation of the protocol solely by a computer using automated/algorithmic methods, such as natural language processing.

Do not distribute for purposes outside of specific activities related to development of FDAMAs114 compliant pieces. Content within this protocol is subject to change based on communication planning and input by external review committees.

Apixaban NON-INTERVENTIONAL STUDY PROTOCOL

In these data sources, individual patient data are not retrieved or validated, and it is not possible to link (i.e., identify a potential association between) a particular product and medical event for any individual. Thus, the minimum criteria for reporting an adverse event (AE) (i.e., identifiable patient, identifiable reporter, a suspect product, and event) cannot be met.

# **COMMUNICATION OF ISSUES**

In the event of any prohibition or restriction imposed (eg, clinical hold) by an applicable Competent Authority in any area of the world, or if the investigator is aware of any new information which might influence the evaluation of the benefits and risks of a Pfizer product, Pfizer should be informed immediately.

In addition, the investigator will inform Pfizer immediately of any urgent safety measures taken by the investigator to protect the study patients against any immediate hazard and of any serious breaches of this NI study protocol of which the investigator becomes aware.

Do not distribute for purposes outside of specific activities related to development of FDAMAs114 compliant pieces. Content within this protocol is subject to change based on communication planning and input by external review committees.

Apixaban NON-INTERVENTIONAL STUDY PROTOCOL

# **12.** List of Tables

- Table 1. Baseline Variables
- Table 2. Clinical Outcome Variables
- Table 3. Health Care Resource Utilization and Cost Outcome Variables

# 13. List of Figures

Figures 1-3. Study Time Periods (for illustration purposes, may not be proportional)

# **ANNEX 1. List of Standalone Documents**

Not applicable.

# **ANNEX 2. Additional Information**

Do not distribute for purposes outside of specific activities related to development of FDAMAs114 compliant pieces. Content within this protocol is subject to change based on communication planning and input by external review committees.

Pfizer Confidential

Page 37 of 37
